Trendelenburg, abdominal insufflation and time to completion of cystoscopy. A prospective randomized trial.

NCT05786391

Version Date: 02/28/2023

Protocol Title: Trendelenburg, abdominal insufflation and time to completion of cystoscopy. A prospective randomized trial.

Principal investigator: [name] (Gynecology Faculty)

Statistician: [name]

Study coordinator: [name]

Population: 136 female patients undergoing a planned cystoscopy after Minimally

Invasive Gynecological procedure.

Number of sites: Two sites MHH-TMC and LBJ.

Study duration: 2 years

Subject duration: 6 weeks

General Information (PICO)

This is a randomized controlled trial assessing time to completion of cystoscopy in seconds after minimally invasive gynecologic surgery

We seek to compare the efficiency of the cystoscopy with two interventions: after two interventions:

- 1- patient position during the cystoscopy (Trendelenburg (head down) or flat)
- 2- Abdominal insufflation (insufflation versus no insufflation).

Both interventions are used as usual care and depend on surgeon preference without evidence why one would faster at completing the cystoscopy. Also note that these two interventions are performed multiple times during the surgery itself and outside the cystoscopy procedure routinely.

Our main objective is to assess which intervention or combination of interventions is more efficient

Background

latrogenic injury to the genitourinary tract is a rare, but significant cause of morbidity in patients undergoing gynecologic surgery for benign indications.1–3 In 2012, the American Association of Gynecologic Laparoscopists recommended that routine cystoscopy be performed after all laparoscopic hysterectomies, whereas the American College of Obstetricians and Gynecologists limited the endorsement to prolapse and incontinence procedures.4,5 Universal cystoscopy, where all women undergoing hysterectomy undergo cystoscopy, has been advocated because as many as 75% of genitourinary injuries occur in women without identifiable risk factors.

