Continuous variables are described with mean (SD) or median (range) depending on the distribution of the data. Statistical tests for continuous data were based on 1-way analysis of variance for normally distributed data, or the Kruskal-Wallis test for nonnormal data. This is determined by histogram plots and Levene test. Categorical variables are described with numbers (percentages) and compared using the χ^2 test. All statistical tests were 2-tailed, and were based on the intent-to-treat principle.

Sample size analysis

Median and IQR cystoscopy duration is 168 (86-286) seconds⁸, a clinically significant improvement in cystoscopy times would be 108 (69-160).

	Insufflation -	Insufflation +
Flat	Group1	Group2
T-Berg	Group3	Group4

Using analysis of variance, 28 subjects in each arm for a total of 112 subjects would be needed to detect an effect size of > 60 seconds, with 80% power and a 2-tailed alpha of 0.05 to achieve statistical significance using the frequentist method. To account for 20% drop outs, we will include 34 patients in each group for a total of 136 cystoscopy procedures,

The one minute decrease in operative time is used based on prior studies showing that the use of "Lasix" intraoperatively can significantly reduce cystoscopy duration by about 78 seconds.⁸

- CONSORT diagram will be performed
- We will evaluate for the presence of interaction between the different interventions as two interventions are employed at the same time.
- Intention to treat analysis will be performed
- All unadjusted outcomes will be reported descriptively (mean SD/ median IQR)
- For all outcomes, we will conduct intent-to-treat Bayesian analysis to calculate probabilities of intervention benefits and harms. We will use neutral priors and exclude large treatment effects. We will report posterior medians of group differences, their corresponding 95% credible intervals, and probability of treatment benefit.

Funding:

IRB NUMBER: HSC-MS-22-1081
IRB APPROVAL DATE: 02/28/2023

None

OVERSIGHT RESPONSIBILITIES

Oversight of the trial is provided by the Principal Investigator (PI), [name] and Co-investigators Drs [name] and [name].

Ethics

- IRB approval will be sought for this study, and admin Approval sought from Harris Health and MHH approval as well as a departmental review.

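### The 20% dropout allowance is miscalculated: 34 per group less 20% leaves 27.2 (108.8 in total), short of the 28 (112) the plan requires

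*Combined protocol and SAP*

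**What the plan says.** Under Sample size analysis the plan states the evaluable number: "28 subjects in each arm for a total of 112 subjects would be needed to detect an effect size of > 60 seconds". The target power is 80% at a two-sided 5% significance level. The same section then sets the enrolment: "To account for 20% drop outs, we will include 34 patients in each group for a total of 136 cystoscopy procedures". The Population line at the start of the protocol repeats that total as "136 female patients undergoing a planned cystoscopy", so 136 is the operative enrolment target.

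No other dropout rate appears, and nothing says what the 20% is a percentage of.

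**The concern.** A dropout allowance is meant to ensure that, if the assumed share of enrolled patients is lost, the number needed for the stated power remains. Here the required number (112), the assumed loss (20%) and the enrolment (136) do not fit together: with 136 enrolled and 20% lost, fewer than 112 remain.

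What is at stake is the accuracy of the sample size statement and, to a small degree, the power. The plan promises a CONSORT diagram, so enrolled and analysed numbers will be reported beside the planned ones. If losses run exactly at the planned rate, the trial will analyse about 109 patients against a stated need of 112.

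Losses after randomization are plausible. Patients are randomized in the preoperative area, while two listed exclusions, blood loss above 500 mL and extensive ureterolysis, may become known only during surgery. The plan does not say whether such patients would be removed despite the intention-to-treat principle.

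**Working it through.** **Inputs, all from Sample size analysis:** required n = 28 per arm (112 in total); dropout d = 0.20; enrolment 34 per group (136 in total); power 80%; two-sided alpha 0.05; difference 60 seconds (168 to 108).

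**Step 1. Reproduce the plan's figure.**
- n × (1 + d) = 28 × 1.20 = 33.6, rounded up to 34 per group.
- 34 × 4 = 136. This matches the plan exactly, so the plan appears to have added 20% to the required number.

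**Step 2. What that enrolment leaves after a 20% loss.**
- 34 × 0.80 = 27.2 per group, which is 0.8 below 28.
- 136 × 0.80 = 108.8 in total, which is 3.2 below 112.

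**Step 3. The inflation that retains the required number.**
- n / (1 − d) = 28 / 0.80 = 35 per group.
- 112 / 0.80 = 140 in total, 4 more than planned.
- Check: 35 × 0.80 = 28 and 140 × 0.80 = 112.

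**Step 4. The loss that 136 can absorb.**
- 1 − 28/34 = 6/34 = 17.6% per group.
- In total, 136 − 112 = 24 patients, if the losses are spread evenly at 6 per group. A seventh loss in any group takes it to 27.

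**Step 5. Effect on power.** The plan gives medians and IQRs but no SD. The calculation therefore takes the plan at its word that 28 per arm gives 80% power, solves for the SD that makes this true, and recomputes at the smaller n.
- *Main effect of one factor* (2n patients per level, two-sided t test with 4n − 4 degrees of freedom). The noncentrality is 60 / (SD × √(2/(2n))) = 60√n / SD. Power at n = 28 is 80.0% when SD = 112.3 s (noncentrality 60 × 5.292 / 112.3 = 2.83).
- *Four-group one-way ANOVA* (noncentral F with 3 and 4n − 4 degrees of freedom, noncentrality 4nf²). Power at n = 28 is 80.0% when f = 0.318. Because f is calibrated, the result does not depend on the pattern of the four means.

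| Evaluable per arm | Main effect | Four-group ANOVA |
|---|---|---|
| 28 | 80.0% | 80.0% |
| 27.2 | 78.8% | 78.7% |
| 27 | 78.5% | 78.3% |

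The loss is 1.2 to 1.3 points at the expected 27.2 per arm, and 1.5 to 1.7 points if the number is rounded down to 27.

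**The case against.** Four points can be made for the plan.

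- **The 20% is not defined.** If it means 20% added to the required number, 34 and 136 follow exactly. But the sentence gives its purpose as accounting for dropouts, and a dropout rate is ordinarily a share of those enrolled. On that reading the figures do not agree, and the documents offer no other definition.
- **The effect is trivial.** The gap is 0.8 patient per arm and a little over one point of power. This stands. It is smaller than the uncertainty in the 28 itself, which cannot be confirmed without an SD. For example, SDs taken as IQR/1.349 from the plan's two sets of quartiles pool to about 115 s, at which main-effect power with 28 per arm is about 78 to 79%. With the reference quartiles alone (148 s) it is about 57%. This limits the importance of the slip but does not make the stated allowance true.
- **Few primary outcomes may be lost.** The cystoscopy is timed in theatre and the analysis is by intention to treat, so loss during the six-week chart review would not remove a cystoscopy time. This is fair, and actual losses may be well below 20%. The plan nevertheless chose 20% itself.
- **A 17% allowance is worked backwards from the enrolment.** It has no independent basis in the documents, and it keeps 28 in every arm only if no arm loses more than six. This stands as a caution on wording: the restated sentence should give the limit per group.

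**Conclusion.** The point holds. With 34 per group enrolled and 20% of them lost, 27.2 per group and 108.8 in total remain, not the 28 and 112 on which the 80% power is stated to rest. The largest loss that retains 28 per group is 6 of 34, or 17.6%.

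This is a minor correction: one patient per group, four in total, and about 1 to 2 points of power. The head counts rest only on the plan's own figures and on reading 20% as a share of enrolled patients. The power figures also assume that 28 per arm gives exactly 80%, which the plan asserts but does not support with an SD. Whether 28 is itself adequate is a separate question.

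**What to change.** Rewrite the one sentence on dropouts under Sample size analysis. Either version needs no extra patients and no design change:

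- **Keep 136 and restate the allowance.** For example: 34 patients per group (136 in total) retain 28 evaluable per group provided that no group loses more than 6 of its 34 patients (about 17%).
- **Keep 20% and restate the yield.** State that about 27 per group (108 in total) are expected to be evaluable, and give the power at that number: roughly 78% to 79% if 28 per arm gives 80%, to be recomputed with the SD actually used.

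The cost is a slightly less favourable allowance or power statement. If the team wants both the 20% allowance and 112 evaluable patients, the enrolment would have to be 35 per group (140 in total), four more patients, and the Population line would need the same change.
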